#### **6.10.3.4 Clinical Cure Rate**

Clinical cure rate is defined as resolution of all scabies signs and symptoms present at Baseline, no new scabies signs and symptoms and no evidence of mites by dermoscopy.

Clinical cure rate will be assessed at Days 7, 14 and 28. At each of these visits, a subject will be considered a responder, as determined by the clinician reported scabies signs and symptoms, if region status is 'Region clear from previous assessment', for each anatomical region assessed at that visit.

For each subject, imputation of missing assessments will be applied as follows. Where the scabies signs and symptoms assessment has been completed for a visit but this includes a missing assessment for a region previously assessed at an earlier time point, the region status will be imputed using the most recent previous assessment for the respective region (last observation carried forward). However, if the scabies signs and symptoms assessment has not been completed for a visit, or the assessments for all regions previously assessed are missing, no imputation will be applied and the subject will be excluded from the denominator for clinical cure rate at that visit.

Where rescue medication has been taken (identified on the concomitant medications page of the eCRF), any assessment indicating clinical cure response subsequent to the start date of rescue medication will be ignored and the subject will be considered a non-responder. Visit responses identified at any visit prior to or on the start date of rescue medication for the subject will be unaffected.

The number and percentage of responders, together with the Clopper-Pearson 95% CI for the percentage, will be presented for each dose group at each post-Baseline visit. The denominator for all percentages will be the number of subjects with a non-missing scabies signs and symptoms assessment for the respective dose group and visit and this will also be presented in the summary.

A flag will be added to the listing of scabies signs and symptoms data to indicate subjects identified as responders at each time point.

Following review of the above summaries, additional post hoc analyses may be considered, for example sensitivity analyses repeating the above clinical cure rate summary without imputation for missing assessments or the use of rescue medication. Any post-hoc analyses to be performed will be fully defined in a SAP Addendum prior to conducting the analyses.

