## 3 SAMPLE SIZE

The sample size chosen for this study, approximately 6 subjects per dose group, was selected to be practical and an adequate sample size for full characterization of PK profile across the dose ranges studied. Sample size was not based on formal power considerations with respect to statistical hypothesis testing.

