  - a. Where rescue medication has been taken (identified on the concomitant medications page of the eCRF), any mite death occurring after the start date of rescue medication will be ignored and the mite will continue to be considered alive. If the mite has already died prior to or on the start date of rescue medication, it will be considered dead for all subsequent visits as stated here.

3. Should the RCM responses indicate a status of 'live' at an assessment occurring after an assessment with a status of 'dead', this will be assumed to be a new infection and thus ignored, i.e. the mite identified at Baseline will still be assumed to have died. This will therefore not impact the analysis of the primary efficacy endpoints.
4. Where data are missing for any of the responses required to determine the status of a mite and therefore the mite status cannot be established, the status of the mite will be assumed not to have changed from the previous non-missing assessment (i.e. the last observation will be carried forward). This includes where a subject withdraws early, in which case the last observation will be carried forward for all remaining visits. Where the last observation is carried forward, this will still be subject to the above rules 1 to 3.

These imputation methods will be applied to all missing adult mite assessments, regardless of the number of lesions for which data are missing for a subject at a timepoint. If data are missing at the subject level (i.e. the RCM assessment is not completed for any lesion at a timepoint for a subject), all mites being evaluated will have their status imputed and therefore no subjects will be missing in the primary analysis summaries presented at each post-Baseline visit.

It should be noted that the above rules may not be exhaustive. If any ambiguity remains in the status of the mite after applying these rules, subject data will be reviewed on a case-by-case basis prior to breaking the blind.

All analyses of the dead/alive response described in the SAP for the primary endpoints will use the values obtained after applying the strategies for any imputation where there is ambiguity or missing data. Similarly references to 'first/last time point where dead/alive' refer to the first/last occurrence once these imputations have been applied. Following review of these analyses, post hoc sensitivity analyses may be considered to assess the impact of these imputations, as described in [Section 6.10.1.6](#).

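### Clinical cure at Day 28: a subject who took rescue medication and has no Day 28 assessment leaves the denominator, although the SAP's own rule allows only non-response

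*SAP*

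**What the plan says.** SAP 6.10.3.4 sets the rules: "Clinical cure rate will be assessed at Days 7, 14 and 28". A subject is a responder "if region status is 'Region clear from previous assessment', for each anatomical region assessed at that visit".

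Three further rules in that section decide who is counted.

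- **Missing data.** If the visit's assessment was completed but an earlier region is missing, that region's last status is carried forward. If the assessment was not completed, or every previously assessed region is missing, "no imputation will be applied and the subject will be excluded from the denominator for clinical cure rate at that visit".
- **Rescue.** After rescue medication, "any assessment indicating clinical cure response subsequent to the start date of rescue medication will be ignored and the subject will be considered a non-responder". Visits on or before the rescue start date are unaffected.
- **Denominator.** Only subjects with a non-missing signs-and-symptoms assessment at the visit are counted. No exception is made for rescued subjects.

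The primary endpoint is handled differently. Under SAP 6.10.1.3, missing mite status is carried forward so that no subject is missing at any visit. After rescue, "any mite death occurring after the start date of rescue medication will be ignored and the mite will continue to be considered alive"; mites that died on or before the rescue start date stay dead.

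On size, SAP 3 says that the sample, "approximately 6 subjects per dose group, was selected to be practical", and adds: "Sample size was not based on formal power considerations with respect to statistical hypothesis testing".

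**The concern.** The rescue clause is triggered by an assessment. With no assessment there is nothing to override, so the exclusion and denominator sentences take over. Two rescued subjects who differ only in whether they attended Day 28 are then treated differently: one is a non-responder, the other disappears.

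That sits badly with the SAP's evident intent. SAP 6.10.3 makes clinical cure the one exploratory endpoint whose result depends on rescue. Protocol 11.2.3 allows rescue only after mites are confirmed by RCM, from Day 14. There is also a built-in route to a missing Day 28 assessment: Protocol 14.2 lets the investigator withdraw a subject for treatment failure, and SAP 6.4 maps data collected at early withdrawal to a separate visit, not to Day 28.

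At stake is the Day 28 cure rate by dose in a study meant to choose a dose. The cure results and the mite results could also rest on different subjects.

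**Working it through.** **Step 1. Apply the rules to a subject rescued after Day 14 and before Day 28.**

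| Day 28 signs assessment | Rule that applies | Result |
|---|---|---|
| Done, not cured | Responder definition | Non-responder, counted |
| Done, cured | Rescue clause | Non-responder, counted |
| Not done | Exclusion and denominator sentences | Not counted |

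No row gives a responder. The outcome is settled once rescue starts, yet the third row removes the subject. Because rescue may be offered only from Day 14, and visits on or before its start date are unaffected, only the Day 28 rate is touched.

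**Step 2. Size.** The documents give no expected cure rate, missed-visit rate or power, so there is no figure to reproduce. Inputs: 6 subjects per dose group (SAP 3) and exact Clopper-Pearson 95% limits (SAP 6.10.3.4). Assumption: m rescued subjects in a group lack a Day 28 assessment. With x cures, the shift in the rate is

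x/(6 − m) − x/6 = x·m / [6(6 − m)].

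| Cures x | All 6 kept | m = 1 dropped | m = 2 dropped |
|---|---|---|---|
| 0 | 0/6 = 0% (0–45.9) | 0/5 = 0% (0–52.2) | 0/4 = 0% (0–60.2) |
| 1 | 1/6 = 16.7% (0.4–64.1) | 1/5 = 20.0% (0.5–71.6) | 1/4 = 25.0% (0.6–80.6) |
| 2 | 2/6 = 33.3% (4.3–77.7) | 2/5 = 40.0% (5.3–85.3) | 2/4 = 50.0% (6.8–93.2) |
| 3 | 3/6 = 50.0% (11.8–88.2) | 3/5 = 60.0% (14.7–94.7) | 3/4 = 75.0% (19.4–99.4) |
| 4 | 4/6 = 66.7% (22.3–95.7) | 4/5 = 80.0% (28.4–99.5) | 4/4 = 100% (39.8–100) |

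For m = 1 the shifts are 0, 3.3, 6.7, 10.0 and 13.3 points.

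**Step 3. Range over an assumed missed-visit rate.** Suppose every uncured subject is rescued and a share q of them lack Day 28. The rate reported in the long run is p / [1 − (1 − p)q], where p is the true rate.

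| True rate p | Bias at q = 10% | q = 25% | q = 50% |
|---|---|---|---|
| 0% | 0 | 0 | 0 |
| 20% | +1.7 | +5.0 | +13.3 |
| 50% | +2.6 | +7.1 | +16.7 |
| 80% | +1.6 | +4.2 | +8.9 |

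All values are percentage points. They are upper values for each q, because not every uncured subject need be rescued.

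**Step 4. Direction of the dose comparison.** Take 2/6 against 5/6, a difference of 50.0 points. One drop in the weaker group gives 83.3 − 40.0 = 43.3. One drop in the stronger group gives 5/5 = 100%, and 100 − 33.3 = 66.7. The contrast can shrink or grow.

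**Step 5. Secondary point.** At a completed visit, a cleared region that was not entered again is carried forward as clear if only some earlier regions are missing. If all of them are missing, the subject is excluded. On that wording a subject with every region already clear could be dropped (5/6 = 83.3% becomes 4/5 = 80.0%). So could a subject whose only entry is a newly affected region, who is plainly a non-responder. Whether either case arises depends on whether the eCRF makes the site enter a cleared region again. The documents do not say.

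**The case against.** The strongest reply is that this is narrow and visible. It concerns one visit of an exploratory, descriptive endpoint, and it needs both rescue and a missed visit. The denominator is printed, rescue is tabulated by dose group (SAP 6.8.1), and all signs data are listed. Leaving missing data out is also the protocol's default (Protocol 15.4.2 and 15.7.9); imputing the primary endpoint is the declared departure (SAP 6.15). All of this stands, and it limits the weight of the point. It does not answer it. A printed denominator shows that a subject is absent, not that the status was already settled. The sensitivity analyses named in 6.10.3.4 are optional and post hoc, and they remove the imputation or the rescue rule without restoring these subjects.

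A reader might infer three stronger things, which the documents do not support.

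- **That cure rates are inflated most in the weakest doses.** For a given number of drops the shift grows with the number of cures and is zero where there are none. The inference needs missed visits to be concentrated in weak groups. That is plausible, but no figure supports it.
- **That fully cleared subjects are dropped, lowering rates where the drug works.** This rests on an eCRF convention that is not given. The clear status is itself a recorded region status, which is consistent with cleared regions being entered again. Protocol 5.4.3 also treats 28 days as a minimum for all symptoms to resolve, so early full clearance may be uncommon.
- **That every missing visit should count as failure.** Visits missed because of COVID-19 would then become drug failures: 5/5 = 100% becomes 5/6 = 83%. Protocol 9.3.7 also allows such subjects to be replaced, so a replacement could be counted beside an original scored as a failure.

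**Conclusion.** The point holds for rescued subjects at Day 28. As written, SAP 6.10.3.4 removes a subject who took rescue medication before Day 28 and has no Day 28 assessment, although its own rule leaves non-response as the only possible result. In a group of 6 with at least one cure and one such subject, the reported rate rises by 3.3 points (one cure) to 13.3 points (four cures). In a group with no cures only the upper limit moves, from 45.9% to 52.2%. These sizes assume 6 per group and one affected subject; how often that happens is unknown. The intervals are wide either way, so this is worth correcting because the correction is nearly free, not because it threatens the trial. The point about regions not entered again is a wording gap whose effect depends on the eCRF.

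**What to change.** In SAP 6.10.3.4:

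1. State that a subject counts as a non-responder, and stays in the denominator, at every scheduled visit after the rescue start date, whether or not an assessment was done. A missed visit has no assessment date, so say which date is compared with the rescue start; the target date of the visit would serve.
2. Amend the exclusion and denominator sentences to carry this exception.
3. For a completed visit at which no previously assessed region was entered again, apply the region-level carry-forward already in the section, and score any newly affected region as non-response. If the eCRF forces cleared regions to be entered again, a sentence saying so is enough.
4. If an analysis counting all other missing visits as non-response is wanted, pre-specify it as a sensitivity analysis and say how replaced subjects enter it. It should not be the main rule.

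The cost is a few sentences and a short change to one derivation. No new data are needed, and visits and treatment are unaffected. The wording should be settled before the blind is broken for the Day 28 analysis.

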### **6.11 Multiplicity**

Given the exploratory nature of the study, no adjustment for multiple comparisons will be made.

### **6.12 Pharmacokinetics**

Plasma for determining the pharmacokinetics of moxidectin will be collected at Baseline (pre-dose), Hours 2, 3, 4, 8, 24, 48 and 72, and at Days 7, 14 and 28.

A separate PKAP will describe the reporting of PK concentrations as well as the derivation and reporting of PK parameters.

### **6.13 Pharmacodynamics**

Details will be included in the separate PKAP regarding analysis of the relationship between efficacy endpoints and plasma concentrations of moxidectin.

### **6.14 Safety Evaluation**

The primary safety endpoint is the assessment of incidence and severity of AEs, physical examinations, and measurement of vital signs up to and including Week 12, and laboratory safety parameters up to and including Day 28.

Details regarding the evaluation of this data are given in the following respective sections.

### 6.14.1 Adverse Events

Adverse events (AEs) will be coded using the latest MedDRA dictionary version in place at the time of analysis and documented in the DMP. The version used will be indicated in the data summaries and listings. If updates to later versions are required during the study, this will be reflected in the DMP and the outputs.

A treatment-emergent adverse event (TEAE) is defined as an AE that started on or after the start of the administration study drug or worsened after study drug exposure. If adverse event dates are incomplete and it is not clear whether the adverse event was treatment-emergent, it will be assumed to be treatment-emergent.

A study drug-related TEAE is defined as a TEAE that is possibly, probably or definitely related to the study drug. If the TEAE has a missing relationship it is assumed to be related to the study drug for analysis purposes.

Each AE will be graded for severity using the FDA Guidance for Industry: Toxicity Grading Scale for Healthy Adult and Adolescent volunteers Enrolled in Preventive Vaccine Clinical Trials. Details regarding this grading are given in Appendix 18.1 of the protocol. For AEs not specifically identified in this grading table, Section 12.2.1 Table 10 of the protocol will be used to apply the severity grades.

A summary table will present the following:

- TEAEs (number of events and number of subjects);
- Serious TEAEs (number of events and number of subjects);
- Serious study drug-related TEAEs (number of events and number of subjects);
- TEAEs by severity grade (Grade 1 – 4) (number of events and number of subjects);
- TEAEs by relationship to study drug (Unrelated, Unlikely, Possible, Probably, Definite) and the pooled study drug related category (Related/Unrelated) (number of events and number of subjects);
- TEAEs leading to withdrawal from study (number of subjects only);
- TEAEs leading to death (number of subjects only).

In the above summaries, if a subject experienced more than one TEAE, the subject will be counted once using the most related event for the “by relationship to study drug” and “study drug-related” summaries and at the worst severity for the “by severity grade” summary.

The following tables will be presented:

- TEAEs by System Organ Class (SOC) and Preferred Term (PT);
- TEAEs by PT;
- TEAEs by SOC, PT and severity grade;

For all of the above, SOC and PT will be presented in decreasing frequency of the total number of subjects with TEAEs.

Further details of the above three tables are given below:

1. If a subject experienced more than one TEAE, the subject will be counted once for each SOC and once for each PT.

2. If a subject experienced more than one TEAE the subject will be counted once for each PT.
3. If a subject experienced more than one TEAE, the subject will be counted once for each SOC and once for each PT at the worst severity grade.

Adverse event data will be listed in full and this will also include a treatment emergent flag, the time of onset and cessation of event relative to dosing of study drug and duration of AE.

#### **6.14.2 Clinical Laboratory Evaluation**

All laboratory values will be converted to the International System of Units (SI) for the purposes of summary and listing.

Observed values and change from Baseline in hematology and biochemistry assessments will be summarized descriptively over time by dose group.

Hematology and biochemistry data will be listed separately including change from Baseline, flagging all out of range values. Toxicity grades will be derived, where possible, for each hematology and biochemistry result as described in Section 18.1 of the protocol and these derived grades will be included in the listings. Parameters will be presented in the same order as the eCRF.

#### **6.14.3 Vital Signs**

Vital sign observed values will be summarized over time by parameter (unit) and dose group.

Weight, collected at Baseline and Week 12, will be included in the vital signs summaries and listing.

Oral and aural body temperature measurements will be summarized and listed as separate parameters within the outputs.

All vital sign data will be listed.

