### 15.6.4 Safety Endpoints

- Incidence and severity of treatment emergent adverse events (TEAEs)
- Incidence of serious TEAEs
- Incidence of TEAEs leading to study withdrawal and/or death
- Changes from baseline in laboratory assessments, vital signs, and physical exams

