### **15.7.6.2 Laboratory Assessments**

Summary statistics at each time point and changes from Baseline will be provided by dose group and overall for laboratory assessments. For continuous assessments, means, SDs, medians, minimums and maximums will be provided. For categorical assessments, the number and percent of subjects in each category will be provided. Shift tables may also be calculated. All laboratory assessments will be included in line listings. Further details will be provided in the SAP.

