### **15.7.6.3 Vital Signs and Physical Exams**

The analysis of vital signs and physical exams will be similar to laboratory assessments.

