### **6.15 Changes from the Protocol Planned Analysis**

- The definition of the FAS has been amended to remove the statement regarding the requirement for 'observed data for the particular analysis undertaken'. Instead, the inclusion/exclusion of subjects with missing data in analyses and summaries of the relevant endpoints on the FAS is addressed via the methods for handling missing data, as described in the respective sections of this SAP.

In addition, some imputation of missing data has been incorporated with respect to analysis and summary of the primary endpoint, rather than exclusion of any subjects with missing observations. These changes were considered more appropriate to ensure closer adherence to the intent to treat principle as well as to ensure clarity regarding the subjects included in the population and in each respective analysis.

- The exploratory endpoint 'presence of eggs and scybala in burrows' has been addressed via the summary of 'mite stages visible by RCM'.

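### SAP 6.14.3 plans summaries of observed vital-sign values only, although Protocol 15.6.4 names change from baseline as a safety endpoint, and SAP 6.15 does not declare the difference

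*SAP*

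**What the plan says.** Protocol 15.6.4 lists among the safety endpoints: "Changes from baseline in laboratory assessments, vital signs, and physical exams". Protocol 15.7.6.2 gives the laboratory method: "Summary statistics at each time point and changes from Baseline will be provided by dose group and overall for laboratory assessments". Protocol 15.7.6.3 extends it: "The analysis of vital signs and physical exams will be similar to laboratory assessments".

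The SAP carries this out for laboratory data. SAP 6.14.2 states: "Observed values and change from Baseline in hematology and biochemistry assessments will be summarized descriptively over time by dose group", and its listing also includes change from Baseline.

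For vital signs, SAP 6.14.3 states: "Vital sign observed values will be summarized over time by parameter (unit) and dose group". On the listing it says only: "All vital sign data will be listed". It adds weight to the vital-sign outputs and separates temperature by method: "Oral and aural body temperature measurements will be summarized and listed as separate parameters within the outputs".

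SAP 6.15, headed "Changes from the Protocol Planned Analysis", covers the FAS definition, imputation for the primary endpoint, and where eggs and scybala are summarized. Vital signs do not appear there.

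**The concern.** A summary that the protocol names as a safety endpoint is missing from the text of the plan meant to deliver it, and the section for such departures is silent. The SAP section immediately before handles laboratory data as the protocol asks, so the wording for vital signs does not read as shorthand.

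Safety is a primary objective, and Protocol 15.2 looks for a dose with good parasitological effect and an acceptable safety profile. Scheduled ECGs stop at Screening (Protocol Table 1), and ECG data are not in the eCRF (SAP 6.14.4). Blood pressure and pulse are therefore the only scheduled post-dose cardiovascular measurements. This is the first study of moxidectin in scabies and it has no comparator. With about six subjects per arm, observed-value tables mix differences between people with changes within a person, and the change is what the endpoint asks for.

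**Working it through.** The plan gives no figure to reproduce. The check compares texts, then counts what is left out, then asks whether the planned tables could stand in for it.

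**1. Texts side by side**

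| | Laboratory data | Vital signs |
|---|---|---|
| Protocol endpoint (15.6.4) | Change from baseline | Change from baseline |
| Protocol method | Values and change (15.7.6.2) | Similar to laboratory data (15.7.6.3) |
| SAP tables | Observed and change (6.14.2) | Observed only (6.14.3) |
| SAP listing | Change included (6.14.2) | Change not mentioned (6.14.3) |
| Declared in SAP 6.15 | No departure to declare | Not mentioned |

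The word *similar* in Protocol 15.7.6.3 allows some latitude in method, but Protocol 15.6.4 names the endpoint directly. No new data are needed: vital signs are taken pre-dose (Protocol Table 2), and SAP 6.2 defines Baseline for all variables.

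**2. Count of unsummarized changes**

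- Parameters (Protocol 9.4.4, with blood pressure as two): systolic and diastolic pressure, pulse, respiratory rate, temperature = 5.
- Post-dose times (Protocol Tables 1 and 2): Hours 8, 24 and 72; Days 7, 14 and 28; Week 12 = 7.
- 5 × 7 = 35. Weight at Week 12, which the SAP groups with vital signs, makes 36.
- By Day 28: 5 × 6 = 30. At Week 12: 5 + 1 = 6.

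**3. Can observed-value tables replace change?**

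With complete data, mean change equals the difference between the visit means. The other statistics do not follow. Var(change) = Var(Baseline) + Var(post) − 2 Cov(Baseline, post), and the tables do not show the covariance. The median, minimum and maximum of change also depend on how the values pair up within subjects.

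An illustration with invented systolic values (mmHg), six subjects per arm and the same Baseline in both arms:

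- Baseline: 108, 112, 116, 120, 124, 128 (mean 118, SD 7.48).
- Arm A, Hour 24: 106, 110, 114, 118, 122, 126.
- Arm B, Hour 24: 110, 114, 118, 122, 126, 106.

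The Hour 24 values are the same set in both arms, so both tables show mean 116, SD 7.48, minimum 106, median 116, maximum 126. The changes differ:

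- Arm A: −2 in every subject; mean −2, SD 0.
- Arm B: +2 in five subjects and −22 in one. Mean = (5 × 2 − 22)/6 = −2. SD = √[(5 × 4² + 20²)/5] = √96 = 9.80. Minimum −22, median +2.

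The toxicity scale would not show the difference either. The hypotension grades in Protocol Appendix 18.1 are absolute, with Grade 1 at 85–89 mmHg systolic, so 106 is ungraded.

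**The case against.** The strongest reply is that little is lost. All vital-sign values are listed by dose group, subject and time (SAP 6.4, 6.14.3), Baseline is defined, and with about six subjects per arm anyone can derive the changes. The drop of 22 mmHg in the illustration would be visible in one subject's listing rows. The protocol rules out inferential safety analysis and leaves detailed methods to the SAP (15.1). The primary safety endpoint, in Protocol 6.2.1 and SAP 2.2, speaks only of measuring vital signs. The shells are a separate document (SAP 1) and could contain change columns. All of this stands and limits the size of the point. It does not remove the mismatch between Protocol 15.6.4 and the SAP text.

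A reader might infer that the omission hides a known cardiovascular signal. Protocol Table 6 reports hypotension in 30% on moxidectin against 25% on ivermectin, and tachycardia in 39% against 30%, in the Phase III onchocerciasis study. The documents do not support that inference:

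- Most of those subjects had orthostatic events: 333 of 382 with tachycardia (87%) and 212 of 289 with hypotension (73%). This trial takes readings supine (Protocol Tables 1 and 2) or semi-supine (Protocol 9.4.4) and schedules none standing, so change in these readings could not show an orthostatic event.
- Supine readings could in principle bear on the non-orthostatic part, which was smaller: tachycardia in 179 of 978 (18%) against 57 of 494 (12%). The two forms overlap, since 333 + 179 = 512 exceeds 382.
- Protocol 5.4.3 attributes the onchocerciasis reactions to dying microfilariae and expects a healthy-volunteer profile in scabies. Protocol 5.3.2.2.1 reports no clinically relevant or treatment-related vital-sign changes at 3 to 36 mg in healthy volunteers.

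A reader might also infer that laboratory toxicity grades must be counted by dose, or that worst post-dose values, including unscheduled ones, must be tabulated. The protocol requires neither. Shift tables are optional in Protocol 15.7.6.2; grades, changes and out-of-range flags are listed; and clinically significant findings reach the adverse-event tables. These are presentation choices and form no part of this point.

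**Conclusion.** The point holds as a mismatch between protocol and SAP. The SAP text plans no change-from-Baseline summary or listing for vital signs, contrary to Protocol 15.6.4 and 15.7.6.3, and SAP 6.15 does not say so. What goes unsummarized is 36 parameter-by-visit changes, including their SD, median and range, which observed-value tables cannot supply.

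The practical impact is modest. Changes can be derived from the listings, safety is descriptive, and nothing in the documents shows that the omission would alter the choice of dose or a safety conclusion. The mismatch itself rests on the text alone. The practical gap assumes that the unseen shells do not already include change; if they do, only the SAP wording needs correcting. The illustration shows what observed-value tables can conceal and predicts nothing about this trial's data.

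**What to change.** In SAP 6.14.3:

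- Extend the first sentence to cover both observed values and change from Baseline, for vital signs and weight, keeping its breakdown by parameter and dose group.
- Add change from Baseline to the vital-sign listing.
- Compute temperature change only where the Baseline and post-dose readings used the same method, oral or aural, and show the number of such pairs. Otherwise the difference mixes method with change.

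If change is left out on purpose, add a line with the reason to SAP 6.15. Align the shells with whichever is chosen.

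The Week 12 rerun needs no new provision, because SAP 5.2 already includes vital signs and weight. The cost is a few words of SAP text, one descriptive table (or added columns in the existing one) and one listing column, all from data already collected. It is best done before the blind is broken for the Day 28 analysis, since Protocol 15.1 requires later SAP changes to be identified in the study report.
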